## 7.7. Concomitant Therapy

Any medication or vaccine (including over-the-counter or prescription medicines, vitamins, and/or herbal supplements) that the participant is receiving at the time of enrolment or receives during the study must be recorded along with:

- reason for use
- dates of administration including start and end dates
- dosage information including dose and frequency

The Medical Monitor should be contacted if there are any questions regarding concomitant or prior therapy.

The following COPD medications are permitted during the study, at the discretion of the GSK Medical Monitor and/or Investigator:

• Inhaled COPD maintenance medications (e.g. long acting bronchodilator medications (i.e. long-acting muscarinic antagonist [LAMA], long-acting betaagonist [LABA]) and long-acting bronchodilator combination therapies (e.g. LAMA/LABA) and long-acting bronchodilator/inhaled corticosteroid steroid combination (ICS) therapies (e.g. LABA/ICS, LAMA/LABA/ICS)

The following medications are prohibited from the screening visit until after completion of the follow up visit:

- Systemic immunosuppressive medication, including current oral corticosteroids at a dose >5 mg, concurrently or within 28 days preceding the screening visit.
- Acute or chronic use of antibiotics, including macrolides for the prevention or treatment of COPD exacerbations. Examples of chronic use include daily or two-three times per week for at least 3 months.Oral or injectable CYP3A4 or BCRP substrates with narrow therapeutic index (CYP3A4 substrates include, but are not limited to, alfentanil, cyclosporine, dihydroergotamine, ergotamine, fentanyl, pimozide, quinidine, sirolimus, tacrolimus, and theophylline; BCRP substrates includeMethotrexate, mitoxantrone, imatinib, irinotecan, lapatinib, rosuvastatin, sulfasalazine, topotecan.
- Current use of phosphodiesterase-4 inhibitors: Roflumilast, Crisaborole and Apremilast
- Broad spectrum phosphodiesterase inhibitors (e.g. theophylline)
- Raloxifene
- Low molecular weight heparin

GSK will not supply rescue medication. Participants may continue to use and should obtain rescue medication(s) through via their usual route. The following rescue medications may be used:

- Short acting beta agonists (SABA)(e.g., albuterol/salbutamol)
- Short acting muscarinic antagonists (SAMA)(e.g., ipratropium)
- Short acting combination (SABA/SAMA) bronchodilations, (e.g. Duoneb, Combivent)

The use of rescue medications is allowable at any time during the study. Annual influenza vaccine is recommended for patients with COPD but is not required for participation in this study. Influenza vaccination is permitted during the study and should be based on applicable local or national guidelines. Pneumococcal vaccine may also be administered, when indicated, based on applicable local or national guidelines. Additional vaccinations may be administered when indicated. Any vaccination administered during the study should be recorded as a concomitant therapy.

## 7.8. Treatment after the End of the Study

The investigator is responsible for ensuring that consideration has been given to the poststudy care of the participant.

GSK will not provide post-study treatment. There are no plans to provide the study treatment for compassionate use following study completion.

# 8. DISCONTINUATION CRITERIA

## 8.1. Discontinuation of Study Treatment

A participant who discontinues study treatment should return to the clinic only for safety assessments as part of an unscheduled visit (physical examination, 12-lead ECG, vitals, blood tests, urinalysis and concomitant medication review) and to return IP as detailed in the SoA and Section 9.4.

## 8.1.1. Liver Chemistry Stopping Criteria

**Liver chemistry stopping and increased monitoring criteria** have been designed to assure participant safety and evaluate liver event etiology.

[figure not shown]
Discontinuation of study treatment for abnormal liver tests is required when:

• a participant meets one of the conditions outlined in the algorithm

OR

• when in the presence of abnormal liver chemistries not meeting protocolspecified stopping rules, the investigator believes study treatment discontinuation is in the best interest of the participant.

#### Phase II Liver Chemistry Stopping and Increased Monitoring Algorithm

Liver Safety Required Actions and Follow up Assessments Section can be found in Appendix 7

#### 8.1.2. Neutrophil Stopping Criteria

A participant with a peripheral blood neutrophil count  $\leq 0.5 \ge 10^9$ /L that is confirmed on repeat testing will be instructed to discontinue treatment and withdraw from the study. The neutrophil count should be monitored daily until it returns to within the baseline value, as detailed in Appendix 8.

#### 8.1.3. QTc Stopping Criteria

- The *same* QT correction formula *must* be used for *each individual participant* to determine eligibility for and discontinuation from the study. This formula may not be changed or substituted once the participant has been enrolled.
  - For example, if a participant is eligible for the protocol based on QT interval corrected for heart rate by Bazett's formula (QTcB), then QTcB must be used for discontinuation of this individual participant as well.
  - Once the QT correction formula has been chosen for a participant's eligibility, the *same formula* must continue to be used for that participant *for all* QT

interval corrected for heart rate *(QTc) data being collected for data analysis.* Safety ECGs and other non-protocol specified ECGs are an exception.

• The QTc should be based on single or averaged QTc values of triplicate electrocardiograms obtained over a brief (e.g., 5-10 minute) recording period.

A participant who meets either bulleted criteria based on the average of triplicate ECG readings will be withdrawn from study treatment:

- QTc >500 msec OR Uncorrected QT >600 msec
- Change from baseline of QTc >60 msec

For participants with underlying bundle branch block, follow the discontinuation criteria listed below:

Baseline QTc with Bundle Branch Block	Discontinuation QTc with Bundle Branch Block
<450 msec	>500 msec
450 – 480 msec	≥530 msec

See the SoA for data to be collected at the time of treatment discontinuation and followup and for any further evaluations that need to be completed.

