#### **Medical Conditions**

- 1. Primary clinical diagnoses of any of the following relevant lung diseases; asthma, sarcoidosis, tuberculosis, pulmonary fibrosis, severe bronchiectasis or lung cancer
- 2. Known alpha-1-antitrypsin deficiency
- 3. Pulse oximetry <88% at rest at screening. Participants should be tested while breathing room air.
- 4. Participants on long term oxygen therapy (defined as >15 hours/day of oxygen use)
- 5. Unstable co-morbidities (eg cardiovascular disease, active malignancy) which in the opinion of the Investigator would make the participant unsuitable to be enrolled in the study. This includes any abnormality identified on screening bloods or screening ECG which in the opinion of the Investigator would make the participant unsuitable for the study.

- 6. History of sensitivity to any of the study medications, or components thereof or a history of drug or other allergy that, in the opinion of the investigator of GSK medical monitor, contraindicates their participation.
- 7. Current or chronic history of liver disease, or know hepatic or biliary abnormalities (with the exception of Gilbert's syndrome or asymptomatic gallstones).
- 8. Participants with a known or suspected history of alcohol or drug abuse within the last 2 years

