#### Diagnostic assessments

- 17. Participants with a peripheral blood neutrophil count  $< 1.0 \times 10^9$ /L at screening
- 18. Diagnosis of pneumonia (chest X-ray or computed tomography [CT] confirmed) within the 3 months prior to screening
- 19. Chest X-ray (posterior with lateral) or CT scan reveals evidence of a clinically significant abnormality not believed to be due to the presence of COPD (historic data up to 1 year may be used).

- 20. Abnormal and clinically significant 12-lead ECG finding at screening. The investigator will determine the clinical significance of each abnormal ECG finding in relation to the participant's medical history and exclude participants who would be at undue risk by participating in the trial. An abnormal and clinically significant finding that would preclude a participant from entering the trial is defined as a 12-lead tracing that is interpreted as, but not limited to, any of the following:
  - AF with rapid ventricular rate > 120 beats per minute (bpm);
  - sustained or non-sustained ventricular tachycardia (VT)
  - second degree heart block Mobitz type II and third degree heart block (unless pacemaker or defibrillator has been implanted)
  - QT interval corrected for heart rate by Fridericia's formula (QTcF) ≥500 msec in participants with QRS <120 msec and QTcF ≥ 530 millisecond (msec) in participants with QRS ≥120 msec

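### With QRS ≥120 msec, the QTcF entry limit (530 msec) lies above the general stopping limit (QTc >500 msec), so a participant can enter already meeting the stopping rule (minor).

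*Protocol*

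**What the plan says.** **Entry.** Exclusion 20 (Protocol 6.2, Diagnostic assessments) concerns an "Abnormal and clinically significant 12-lead ECG finding at screening". Its QT item has two limits keyed to QRS width: QTcF ≥500 msec when QRS is <120 msec, and "QTcF ≥ 530 millisecond (msec) in participants with QRS ≥120 msec". The list is open, since a disqualifying tracing is one "interpreted as, but not limited to, any of the following", and the investigator judges the significance of each abnormal finding. Exclusion 5 (Medical Conditions) separately lets the investigator exclude for "any abnormality identified on screening bloods or screening ECG".

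**Stopping.** Under Protocol 8.1.3, a participant who meets either of two criteria "based on the average of triplicate ECG readings will be withdrawn from study treatment". The first begins "QTc >500 msec OR" and continues with an uncorrected QT above 600 msec. The second is "Change from baseline of QTc >60 msec". A separate instruction follows: "For participants with underlying bundle branch block, follow the discontinuation criteria listed below". Its table has two rows. A baseline below 450 msec stops at >500 msec, and a baseline of 450–480 msec stops at ≥530 msec. No row covers a higher baseline, and no separate limit exists for wide QRS without bundle branch block.

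**Timing.** The Schedule of Activities places triplicate ECGs at Visits 1, 2 (Day 1) and 4 (Day 14). SAP 5.2 takes the last pre-dose value as the ECG baseline.

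**The concern.** An entry limit and a stopping limit for the same measurement should fit together, so that nobody enters beyond the point at which treatment must stop. For narrow QRS they do. For wide QRS the entry limit is 30 msec higher, but the stopping limit rises with it only for bundle branch block with a baseline of 450–480 msec.

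A wide-QRS participant could thus be randomized, keep the same QTcF throughout, and have to be withdrawn at the first on-treatment ECG although the drug had done nothing. Protocol 8.1.4 makes stopping treatment equivalent to leaving the study. At stake are an avoidable withdrawal that could be read as a drug-related QT signal, and inconsistent handling of bundle branch block between investigators.

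**Working it through.** No figure in the plan needs reproducing. The check sets the entry limits beside the stopping limits.

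**Inputs**
- Mandatory exclusion (Protocol 6.2, exclusion 20): QTcF ≥500 msec if QRS <120 msec; ≥530 msec if QRS ≥120 msec.
- General stop (Protocol 8.1.3): QTc >500 msec.
- Bundle branch block stop (same section): baseline <450 msec, >500 msec; baseline 450–480 msec, ≥530 msec.

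**Conventions.** Values are whole milliseconds. The highest values below mandatory exclusion are then 499 (narrow QRS) and 529 (wide QRS), and the first value meeting the general stop is 501. QTcF is used on both sides, because exclusion 20 is written in QTcF and 8.1.3 carries the eligibility formula forward. The Day 1 baseline is assumed to stay near the screening value.

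**Headroom = first stopping value − highest baseline that can enter in that group**

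| Group | Highest baseline | First stopping value | Headroom (msec) |
|---|---|---|---|
| QRS <120, no block | 499 | 501 | 501 − 499 = +2 |
| QRS ≥120, no block | 529 | 501 | 501 − 529 = −28 |
| Block, baseline 450–480 | 480 | 530 | 530 − 480 = +50 |
| Block, baseline >480, QRS ≥120, general rule as fallback | 529 | 501 | 501 − 529 = −28 |
| Block, baseline >480, QRS <120, general rule as fallback | 499 | 501 | 501 − 499 = +2 |

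**Width of the overlap.** For wide QRS without block, 529 − 501 + 1 = 29 whole-msec values pass the numeric entry limit yet exceed the stopping limit. For narrow QRS there are none.

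**Bundle branch block without a row.** With QRS ≥120 msec this is 481–529, or 529 − 481 + 1 = 49 values. Under the general rule, 501–529 (29 values) conflict at entry and 481–500 (20 values) do not. With QRS <120 msec it is 481–499, or 499 − 481 + 1 = 19 values, none in conflict at entry.

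**Step at 480 msec.** The rise that triggers stopping is 530 − 480 = 50 msec at baseline 480 by the table, and 501 − 481 = 20 msec at baseline 481 by the general rule. Both are below 60 msec, so the step is the same whether or not the change-from-baseline criterion applies in bundle branch block.

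**After the proposed change.** Without block, the highest baseline is 499 whatever the QRS width, giving headroom of 2 msec. With block, the highest baseline is 480, giving headroom of 50 msec, and every enrolled baseline has a table row.

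These are counts of milliseconds, not of participants. The documents give no prevalence for wide QRS or bundle branch block.

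**The case against.** **Discretion at entry.** The 530 msec figure triggers mandatory exclusion; it is not permission to enrol up to 529. Exclusions 5 and 20 both let the investigator turn such a person away, Protocol 8.2 allows withdrawal for safety, and Protocol 9 sends immediate safety concerns to the sponsor. This stands as a reason why the conflict would be rare. It does not bring the two limits into line, and once a participant is enrolled the stopping rule is mandatory and waivers are not allowed.

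**One group or two.** The documents do not define bundle branch block or relate it to QRS ≥120 msec, so the authors may have meant the same conduction-delay group in both places. That is possible. Even so, the table ends at 480 msec and the entry limit at 529, so the conflict at 501–529 msec would remain under the general rule.

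**Is there no threshold at all in bundle branch block above 480 msec?** A reader might infer this from the missing row. The text does not support it: the general criteria are written for any participant, so they are the natural fallback. What is missing is a sentence saying so, and one saying whether the >60 msec change and uncorrected QT >600 msec criteria apply in block. That is mostly missing detail.

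**Direction of the error.** The general rule stops a wide-QRS participant sooner, not later, so the mismatch does not prolong exposure. The risk table in Protocol 3.3.1 lists no QT risk for danirixin. After Day 1 the only scheduled ECG is on Day 14, the last treatment day, so little dosing would be left to stop. All of this stands and keeps the point minor.

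**Too late for this trial.** SAP 3.2 records that the study was stopped early with 19 completers. The correction therefore matters mainly where this text is reused.

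**Conclusion.** The inconsistency is real and minor. With QRS ≥120 msec and no bundle branch block, a QTcF of 501–529 msec passes the numeric entry limit, subject to investigator discretion, and already meets the mandatory stopping rule. In bundle branch block with QRS ≥120 msec the same conflict arises at 501–529 msec if the general rule is the fallback above 480 msec, and the tolerated rise drops from 50 to 20 msec across that boundary.

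Two wider readings are not supported. One is that every participant with QRS ≥120 msec stops at >500 msec: bundle branch block with a baseline of 450–480 msec stops at ≥530 msec. The other is that efficacy conclusions are at risk: few or none of at most 32 randomized participants would be affected, and the primary analysis method does not depend on these limits.

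Confidence is high for the mismatch without block, since it follows from the printed limits. The part on block above 480 msec rests on the fallback reading. Practical effect also depends on the Day 1 value staying near the screening value.

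**What to change.** Change the QT item of exclusion 20 to exclude QTcF ≥500 msec regardless of QRS width, and QTcF >480 msec in participants with bundle branch block. Apply it at screening and again to the pre-dose triplicate ECG at Visit 2, before randomization. Add one sentence to 8.1.3 saying whether the >60 msec change and uncorrected QT >600 msec criteria also apply in bundle branch block.

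No new procedure is needed. The Visit 2 ECG is already scheduled, the Schedule of Activities places baseline assessments before randomization, and Protocol 9.4.3 has the machine measure QRS and QTc automatically. The price is slightly narrower eligibility. The entry limit also becomes stricter for bundle branch block (480 msec) than for wide QRS without it (499 msec), although block has the more lenient stop at 450–480 msec; the reason is only that the stopping table ends at 480.

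The alternative is to keep 530 msec at entry and add stopping thresholds for bundle branch block above 480 msec and for wide QRS without block. That preserves eligibility, but the new thresholds would need a justification that the documents do not provide.

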#### 8.1.4. Temporary Discontinuation

Withdrawal of study treatment requires withdrawal from the study.

#### 8.1.5. Rechallenge

#### 8.1.5.1. Study Treatment Restart or Rechallenge

Study treatment restart or rechallenge after liver chemistry stopping criteria are met by any participant in this study is not allowed.

## 8.2. Withdrawal from the Study

- A participant may withdraw from the study at any time at his/her own request, or may be withdrawn at any time at the discretion of the investigator for safety, behavioral, compliance or administrative reasons.
- If the participant withdraws consent for disclosure of future information, the sponsor may retain and continue to use any data collected before such a withdrawal of consent.
- If a participant withdraws from the study, he/she may request destruction of any samples taken and not tested, and the investigator must document this in the site study records.

- Refer to the SoA for data to be collected at the time of study discontinuation and follow-up and for any further evaluations that need to be completed.
- Any participant who experiences a COPD exacerbation (i.e., associated with antibiotic or steroid use) will be permanently discontinued from study treatment and should return to the clinic for follow-up if possible. Only the safety assessments scheduled for the follow-up visit should be conducted in these participants as described in the SoA (Section 2).

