#### **Treatment Groups and Duration:**

The study will consist of a screening/baseline period of up to 30 days, a 2 week treatment period, and a 1-week follow-up visit. The study duration, including screening and follow-up, is not expected to exceed 2 months for participants in the study.

Study treatment will consist of two groups: danirixin 35mg HBr orally twice daily or matching placebo.

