# 2. SCHEDULE OF ACTIVITIES (SOA)

Procedure	Procedure Pre-Scree and Scree			tment Po (14 days		Follow-up Phone call	Unscheduled visit 	Notes
	V 0	V1	V2	V3	V 4	V5		
Day	Day -30	to -1	D 1	D 7	D14	D 21	As required	
Assessment window				±1d	±1d	± 3d	As required	
Written, informed consent	Х							
Inclusion and exclusion criteria	Х							Recheck clinical status before randomization.
Demography, Medical history	Х							
Baseline COPD assessment test (CAT) score	Х							
Adverse event (AE)/Serious adverse event (SAE) review	Х	+	-=====	======	$\rightarrow$	Х	Х	
Concomitant medication review	Х	←			$\rightarrow$	Х	Х	
Full physical examination including height and weight	Х						Х	
Vital signs	Х	Х	Х	Х	Х		Х	
Volatile organic compound (VOC) measurement	Х3	X 	X5	X3	X3		Х	
Spirometry	Х		Х		Х		Х	
Induced Sputum Samples (including biomarker samples)	Х	X 4	Х	Х	Х		Х	
Spirometry post-Sputum Induction	Х	X 4	Х	Х	Х		Х	
Triplicate 12-lead ECG		Х	Х		Х		Х	
Chest X-ray (historical within 1 year acceptable)		Х						
HIV, Hepatitis B and C screening		X6						
Laboratory assessments (clinical chemistry including liver chemistries, haematology, biomarkers)		х	Х		х		х	
Pharmacokinetic (PK) sample			X7	X8	X7		Х	See footnotes for timings of PK sampling
Genetic sample			Х9					Pre-dose (baseline) sample.
Urinary Pregnancy test (WOCBP only)		X 	X 		X 		X 	
Urinalysis (including biomarker samples)		Х	Х		Х		Х	
Randomization			Х					All baseline assessments at V2 should be completed prior to randomization
Study treatment			Х	$\leftrightarrow$	Х			

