#### 3.3.1. Risk Assessment

Potential Risk of Clinical Significance	Summary of Data/Rationale for Risk	Mitigation Strategy
	Investigational Product (IP) GSK 1325756	
Testicular effects and male fertility	The most sensitive species is the rat. Testicular effects present at doses ≥150 mg/kg/day in the rat include spermatid degeneration, seminiferous tubular degeneration and secondary epididymal changes, including oligo/aspermia and/or epididymal intratubular cellular debris. The no observed adverse effect level (NOAEL) in this study, based on the microscopic findings in the testis, was 50 mg/kg/day for male rats. The systemic exposure margins for the NOAEL for testicular effects in the rat is 7.3-fold for an oral clinical dose of 50 mg twice daily dosing (BID) free base tablet. The testicular effects seen in the rat have also been shown to directly impact on male fertility and the NOAEL for these reproductive effects was 100 mg/kg/day. Refer to IB Section 4.4 for full details No adverse events related to testicular effects have been observed in clinical studies to date.	Standard safety monitoring will be employed. The potential risk of testicular injury has been conveyed in the informed consent. PK modelling predicts that in a participant receiving 35 mg BID of the HBr salt, the risk of exposure exceeding the 2-fold margin for area under the concentration curve from pre-dose to 24 hours post-dose (AUC[0-24] for the NOAEL of testicular effects is low.
Impairment of host defense.	Host defense has not been studied directly in nonclinical studies. However, data in nonclinical species have not identified an increased risk of infection with danirixin. Nonclinical studies in mice and ferrets with two CXCR2	Monitoring of peripheral blood neutrophil count. Stopping criteria: in participants with a
	antagonists in the same chemical class as danirixin have not shown an increase in infections in challenge models	confirmed absolute neutrophil count $\leq 0.5 \text{ x}$ $10^9/\text{L}$ product will be discontinued and

Potential Risk of Clinical Significance	Summary of Data/Rationale for Risk	Mitigation Strategy
	(e.g., influenza viral load).	neutrophil count will be monitored until return to normal.
	Secondary bacterial infections after viral	
	infection have not been directly evaluated in nonclinical studies.	Ongoing assessment of AE/SAEs related to infection. Closely monitor, collect information on and characterize infection

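### Protocol 8.2 limits a participant stopped for a COPD exacerbation to what is scheduled at a follow-up phone call, contradicting the clinic safety visit in 8.1; a stop before V4 then has no required post-dose neutrophil count, liver chemistry or ECG

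*Protocol*

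**What the plan says.** Section 8.2 takes a participant with an exacerbation (one associated with antibiotic or steroid use) off treatment for good and asks for a return to the clinic where feasible. It then restricts what is done there: "Only the safety assessments scheduled for the follow-up visit should be conducted in these participants as described in the SoA (Section 2").

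The synopsis describes "a 2 week treatment period, and a 1-week follow-up visit". In the SoA the corresponding column, V5 on Day 21, is headed "Follow-up Phone call", and the text with the study schematic in 5.1 also calls it a phone call.

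Section 8.1 is the general rule. A participant who discontinues treatment "should return to the clinic only for safety assessments as part of an unscheduled visit (physical examination, 12-lead ECG, vitals, blood tests", with urinalysis and concomitant medication review completing the list, and study medication is to be returned.

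Two other provisions bear on this. Section 8.1.4 states: "Withdrawal of study treatment requires withdrawal from the study". Section 3.3.1 lists "Monitoring of peripheral blood neutrophil count" among the mitigations for impaired host defence.

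**The concern.** Both rules cover the same participant. Section 8.1 applies to everyone who stops treatment; 8.2 is the specific rule for an exacerbation. A site would reasonably follow the specific rule, particularly since section 9 makes adherence to the SoA mandatory and allows no waivers. Section 8.2 also sits badly with itself: it asks for a clinic attendance and then permits only what is scheduled for a phone call.

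What is at stake is a safety check in a group where infection is a live question, on a drug whose listed potential risks include impaired host defence. The neutropenia actions depend on a low count having been found. Section 8.1.2 says "The neutrophil count should be monitored daily until it returns to within the baseline value", but only after a confirmed low value, and Appendix 8 likewise starts from one. If no count is required at the stop, nothing in the schedule would trigger those actions.

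**Working it through.** No statistical calculation applies. The check is to set the SoA against 8.1 and 8.2 and count. The SoA copy in SAP Appendix 2 carries the same marks.

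| Assessment | In the 8.1 list | SoA V5 (phone call) | SoA Unscheduled column | Scheduled after first dose |
|---|---|---|---|---|
| Physical examination | yes | no | yes | none |
| 12-lead ECG | yes | no | yes | V4 |
| Vital signs | yes | no | yes | V3, V4 |
| Blood tests (haematology, chemistry with liver tests) | yes | no | yes | V4 |
| Urinalysis | yes | no | yes | V4 |
| Concomitant medication review | yes | yes | yes | throughout, to V5 |
| AE/SAE review | not listed | yes | yes | throughout, to V5 |

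**Overlap.** The 8.1 list has 6 items. V5 shares 1 of them (concomitant medication review), so 6 − 1 = 5 are missing under 8.2. The Unscheduled column is marked for all 6.

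**Post-dose laboratory tests and ECG.** The laboratory row is marked at V1, V2, V4 and Unscheduled, and is blank at V3 (Day 7) and V5. The ECG row has the same pattern. The SoA puts V2 baseline assessments before randomization, and SAP 5.2 takes the last pre-dose value as baseline for laboratory tests and ECG, so the V2 values are pre-dose. Scheduled post-dose haematology draws are then V3 = 0, V4 = 1, V5 = 0.

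**Consequence for an early stop.** Under 8.1.4 a participant who stops treatment leaves the study, so V4 does not take place. The follow-up content under 8.2 as written adds 0 draws. Required post-dose neutrophil counts, liver chemistries and ECGs are therefore 0 for a stop before V4. Under 8.1 the same participant would have blood tests and an ECG at the unscheduled visit.

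**Exposure at that point.** V4 has a window of ±1 day, so it may fall on Day 13. Day 12 is the last day before the window opens; a stop then follows up to 12 × 2 = 24 tablets.

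**Number affected.** Expected dropout is below 10%. With 24 participants, 0.10 × 24 = 2.4, so at most 2; with 32, 0.10 × 32 = 3.2, so at most 3. These figures cover all reasons for dropout, so exacerbation stops are some part of them. With 3:1 randomization about three in four would be on danirixin.

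**The case against.** The strongest reply is that 8.1 already covers these participants and that the restriction in 8.2 was probably meant only to exclude efficacy procedures such as sputum induction. A clinic return makes little sense if a phone call's content is all that is intended. That is a plausible account of the intent, but it does not alter the text: the column 8.2 points to contains no examination or test, and the section that would supply them is the one 8.2 contradicts.

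Several stronger readings are tempting, and the documents do not support them.

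- *That the SoA has nothing for participants who stop.* Section 8.1.3 says "See the SoA for data to be collected at the time of treatment discontinuation and followup", and there is no column for early withdrawal, although the design figure in SAP 2.3 names such a visit. But the Unscheduled column is marked for every item in the 8.1 list, and 8.1 names that visit type. A dedicated column is a matter of layout. Return of study medication is marked only at V4, but 8.1 asks for it in its own text.
- *That 8.1 provides one scheduled count against none under 8.2.* The 8.1 visit is an unscheduled one, and SoA footnote 2 lets its content follow the need for the visit. The fair contrast is between blood tests that 8.1 asks for and blood tests that 8.2 rules out.
- *That such a participant cannot have a count.* Footnote 2 and section 9 allow unscheduled samples for safety, and Appendix 4 obliges the investigator to arrange evaluations that are medically indicated for an AE. These routes are real, but they rest on judgement.
- *That a known hazard goes unwatched.* Section 3.3.1 reports no neutrophil counts below the lower limit of normal in COPD patients given danirixin for one year, and close monitoring of infection events is a further mitigation.

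It is also fair to say that dropout below 10% is an expectation and not a ceiling, and that SAP 3.2 records early termination with 19 participants completed, which limits the practical use of an amendment in this trial.

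**Conclusion.** The contradiction is real. Followed as written, the rule for exacerbation stops drops five of the six items in 8.1, and with them the only post-dose haematology, liver chemistry and ECG that the protocol would otherwise require of someone stopped before V4. This is an internal inconsistency in a safety rule, and a minor one: few participants are expected to be affected, judgement-based routes to the same tests remain, and no efficacy analysis depends on it. The conclusion assumes that a site applies 8.2 literally, that V2 laboratory tests and ECGs are taken before the first dose, and that a stopped participant does not attend V4.

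**What to change.** In 8.2, replace the restricting sentence with one that points to 8.1, for example: *Assessments in these participants are limited to the safety assessments in Section 8.1 (unscheduled visit: physical examination, 12-lead ECG, vital signs, blood tests including haematology, urinalysis, AE and concomitant medication review, and return of study medication).* This still excludes efficacy procedures. The V5 call and AE collection under 9.2.1 stay as they are.

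The cost is one sentence and a visit that 8.1 already asks for, in roughly 0 to 3 participants if dropout is as expected. AE review is not in the 8.1 list but is already marked in the Unscheduled column. Completers see no change. No analysis changes: under SAP 12.5.2 unscheduled visits are listed and kept out of summaries.

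An Early Withdrawal column in the SoA is optional. If one is added, the SoA copy in SAP Appendix 2 must be updated, and the SAP should say how that visit is displayed.
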